6.7. Appendix 7: MedDRA PT for Diabetic Retinopathy or Maculopathy

The following PT will be used to identify TEAEs of diabetic retinopathy or maculopathy (see Section 4.6.2.1.7):

- *Amaurosis*
- *Amaurosis fugax*
- *Arteriosclerotic retinopathy*
- *Blindness*
- *Blindness transient*
- *Blindness unilateral*
- *Choroidal neovascularisation*
- *Cystoid macular oedema*
- *Detachment of macular retinal pigment epithelium*
- *Detachment of retinal pigment epithelium*
- *Diabetic blindness*
- *Diabetic eye disease*
- *Diabetic retinal oedema*
- *Diabetic retinopathy*
- *Diabetic uveitis*
- *Diplopia*
- *Exudative retinopathy*
- *Eye laser surgery*
- *Fundoscopy*
- *Fundoscopy abnormal*
- *Intra-ocular injection*
- *Macular detachment*
- *Macular oedema*
- *Maculopathy*
- *Noninfective chorioretinitis*
- *Noninfective retinitis*
- *Phacotrabeculectomy*
- *Retinal aneurysm*
- *Retinal arteriovenous malformation*
- *Retinal artery embolism*
- *Retinal artery occlusion*
- *Retinal artery stenosis*
- *Retinal collateral vessels*
- *Retinal cryoablation*
- *Retinal detachment*
- *Retinal exudates*

- *Retinal haemorrhage*
- *Retinal laser coagulation*
- *Retinal neovascularisation*
- *Retinal oedema*
- *Retinal operation*
- *Retinal thickening*
- *Retinal vascular disorder*
- *Retinal vascular occlusion*
- *Retinal vein occlusion*
- *Retinitis*
- *Retinopathy*
- *Retinopathy haemorrhagic*
- *Retinopathy hypertensive*
- *Retinopathy hyperviscosity*
- *Retinopathy proliferative*
- *Scintillating scotoma*
- *Sudden visual loss*
- *Venous stasis retinopathy*
- *Vision blurred*
- *Visual acuity reduced*
- *Visual acuity reduced transiently*
- *Visual impairment, and*
- *Vitrectomy.*

6.8. Appendix 8: MedDRA PT for Peripheral Edema

The analysis of peripheral edema (Section 4.6.2.1.8) will be based on the TEAEs in the following terms:

- *Acute pulmonary oedema*
- *Ascites*
- *Brain oedema*
- *Bronchial oedema*
- *Capillary leak syndrome*
- *Cerebral oedema management*
- *Compression garment application*
- *Cytotoxic oedema*
- *Effusion*
- *Fluid retention*
- *Gastrointestinal oedema*
- *Generalised oedema*
- *Gravitational oedema*
- *Hydraemia*
- *Hypervolaemia*
- *Hypoosmolar state*
- *Lipoedema*
- *Lymphoedema*
- *Negative pressure pulmonary oedema*
- *Non-cardiogenic pulmonary oedema*

- *Non-pitting oedema*
- *Oedema*
- *Oedema blister*
- *Oedema due to cardiac disease*
- *Oedema due to hepatic disease*
- *Oedema due to renal disease*
- *Oedema mucosal*
- *Oedema peripheral*
- *Pelvic fluid collection*
- *Pericardial effusion*
- *Perinephric collection*
- *Perinephric oedema*
- *Peripheral swelling*
- *Pleural effusion*
- *Pulmonary oedema*
- *Retroperitoneal effusion*
- *Retroperitoneal oedema*
- *Skin oedema*
- *Skin swelling*
- *Subdural effusion*
- *Swelling, and*
- *Visceral oedema.*

6.9. Appendix 9: Definition for Persistent-Recurrent Hypoglycemia by Programming

A P-R hypoglycemia based on a programming search in the e-diary database for hypoglycemic events that meet prespecified criteria is defined as a set of hypoglycemic episodes that

- a) starts with the occurrence of a Level 3, or Level 2 hypoglycemic episode (<54 mg/dL [3.0 mmol/L]) and is followed by more episodes of hypoglycemia (<70 mg/dL [3.9 mmol/L]), within the day of the initial episode

AND

- b) is followed by at least 1 episode of hypoglycemia (<70 mg/dL [3.9 mmol/L]) per day, in the next 2 days or longer, and that ends when no hypoglycemia episode occurs for at least 2 days.

An example of a set of hypoglycemic episodes meeting the prespecified criteria of a P-R hypoglycemia event is illustrated in [Figure BDCV.6.1](#).

[figure not shown]

Figure BDCV.6.1. Illustration of persistent-recurrent hypoglycemia by programming.

6.10. Appendix 10: Abnormality Level Criteria for Chemistry and Hematology Laboratory Results

Parameter	Level 1	Level 2	Level 3
General Chemistry			
Sodium, low (mEq/L)	<132	<130	<125
Sodium, high (mEq/L)	>150	>155	>160
Potassium, low (mEq/L)	<3.6	<3.4	<3.0
Potassium, high (mEq/L)	>5.5	>6	>6.5
Chloride, low (mEq/L)	<95	<88	<80
Chloride, high (mEq/L)	>108	>112	>115
Bicarbonate, low (mEq/L)	<20	<18	<15
Bicarbonate, high (mEq/L)	N/A	N/A	>30
Blood urea nitrogen, high (mg/dL)	>23	>27	>31
Calcium, low (mg/dL)	<8.4	<8.0	<7.5
Calcium, high (mg/dL)	>10.5	>11.0	>12.0
Phosphate, low (mg/dL)	<2.5	<2.0	<1.4
Protein (total), low (g/dL)	<6.0	<5.4	<5.0
Albumin, low (g/dL)	<3.1	<2.5	<2.0
Uric Acid (urate), high (mg/dL)	>7.0	NA	NA
Kidney Function			
Creatinine, increase (mg/dL)	$\geq 1.5 \times$ baseline	$\geq 2.0 \times$ baseline	$\geq 3.0 \times$ baseline
eGFR, decrease (ml/min/1.73m ²)	$\geq 25\%$ decrease	$\geq 50\%$ decrease	$\geq 75\%$ decrease
Lipids			
Cholesterol (total), high (mg/dL)	>200	>240	>300
HDL, low (mg/dL), males	<40	<30	<20
HDL, low (mg/dL), females	<50	<40	<20
LDL, high (mg/dL)	>130	>160	>190
Triglycerides, high (mg/dL)	>150	>300	>500
Hematology			
Complete Blood Count			
WBC, low (cells/ μ L)	<3500	<3000	<1000
WBC, high (cells/ μ L)	>10,800	>13,000	>15,000
Hemoglobin, decrease (g/dL)	N/A	>1.5 dec. from baseline	>2 dec. from baseline
Hemoglobin, increase (g/dL)	N/A	>2 inc. from baseline	>3 inc. from baseline
Platelets, low (cells/ μ L)	<140,000	<125,000	<100,000
Hemoglobin, low (g/dL), male	12.5-13.5	<12.5	<10.5
Hemoglobin, low (g/dL), female	11.0 – 12.0	<11	<9.5
WBC Differential			
Lymphocytes, low (cells/ μ L)	<1000	<750	<500
Lymphocytes, high (cells/ μ L)	>4000	>10000	>20000
Neutrophils, low (cells/ μ L)	<2000	<1000	<500
Eosinophils, high (cells/ μ L)	>650	>1500	>5000
Coagulation Studies			
Prothrombin time, increase (sec)	$>1.1 \times$ ULN	$>1.3 \times$ ULN	$>1.5 \times$ ULN

Abbreviations: eGFR = estimated glomerular filtration rate; HDL = high-density lipoprotein; LDL = low-density lipoprotein; NA = not applicable; ULN = upper limit of normal.

Note: For liver enzymes, Lilly defined categories will be used.

6.11. Appendix 11: Empirical Estimation of Relative Event Rate

Traditionally, the Poisson distribution has been assumed to draw inference for the rate of rare events. When the event is rare and the sample size is large, it is known that the overall number of events is approximately from Poisson distribution. However, for some not very rare events such as severe hypoglycemic events in T1D participants, the total number of events may not be distributed from Poisson and may be over-dispersed. Assuming Poisson distribution may significantly underestimate the variance, and therefore may reduce the coverage probability and inflate the type 1 error. An empirical method in estimating the variance of the relative event rate without assuming any distribution on the number of events will be provided in this appendix.

Let X_{ij} denote the count response variable for participant j in treatment group i . Let $Y_i = \sum_j X_{ij}$ be the total number of events for treatment group i , and T_i denote the exposure for treatment group i . Let $i = 0$ for the control group and $i = 1$ for the experimental treatment group. The event rate for treatment group i can be calculated as

$$\hat{r}_i = \frac{Y_i}{T_i}$$

The empirical variance of \hat{r}_i is

$$\widehat{Var}(\hat{r}_i) = T_i^{-2} \widehat{Var}(Y_i) = T_i^{-2} n_i S_i^2,$$

where S_i^2 is the variance of X_{ij} for treatment group i . Using the delta-method, the variance of $\log(\hat{r}_i)$ can be estimated as

$$\widehat{Var}(\log(\hat{r}_i)) = Y_i^{-2} n_i S_i^2$$

The relative rate of the experimental treatment versus the control treatment is estimated as

$$\hat{\lambda} = \frac{\hat{r}_1}{\hat{r}_0}$$

The variances of $\hat{\lambda}$ and $\log(\hat{\lambda})$ are

$$\widehat{Var}(\hat{\lambda}) = \hat{\lambda}^2 \widehat{Var}(\log(\hat{\lambda}))$$

$$\widehat{Var}(\log(\hat{\lambda})) = \widehat{Var}(\log(\hat{r}_0)) + \widehat{Var}(\log(\hat{r}_1)) = Y_0^{-2} n_0 S_0^2 + Y_1^{-2} n_1 S_1^2$$

Assuming $\log(\hat{\lambda})$ is asymptotically from a normal distribution, the $100(1 - \alpha)\%$ confidence interval for $\log(\hat{\lambda})$ can be constructed as

$$\left[\log(\hat{\lambda}) - z_{1-\frac{\alpha}{2}} \sqrt{\widehat{Var}(\log(\hat{\lambda}))}, \log(\hat{\lambda}) + z_{1-\frac{\alpha}{2}} \sqrt{\widehat{Var}(\log(\hat{\lambda}))} \right]$$

Then, the $100(1 - \alpha)\%$ confidence interval for $\hat{\lambda}$ is

$$\left[\hat{\lambda} \exp\left(-z_{1-\frac{\alpha}{2}} \sqrt{\widehat{Var}(\log(\hat{\lambda}))}\right), \hat{\lambda} \exp\left(z_{1-\frac{\alpha}{2}} \sqrt{\widehat{Var}(\log(\hat{\lambda}))}\right) \right] \quad (1)$$

The p-value for testing the null hypothesis of $H_0: \lambda = 1$ is calculated as

$$p = 2\Phi\left(\left|\log(\hat{\lambda})\right|/\sqrt{\widehat{Var}(\log(\hat{\lambda}))}\right) \quad (2)$$

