4.1. General Considerations

Statistical analysis of this study will be the responsibility of Eli Lilly and Company (Lilly) or its designees. Any change to the data analysis methods described in the protocol will require an amendment ONLY if it changes a principal feature of the protocol. Any other changes to the data analysis methods described in the protocol, and the justification for making the change, will be described in this SAP or the clinical study report. Additional exploratory analyses of data will be conducted as deemed appropriate. Statistical analyses for Japan Addendum are described in Appendix 12 (Section 6.13).

Unless otherwise stated, the efficacy analyses will be based on either Efficacy Analysis Set 1 (EAS1, see the definition in Section 3) or Efficacy Analysis Set 2 (EAS2, see the definition in Section 3). For the treatment-regimen estimand, EAS1 will be used. Unless otherwise specified, for the efficacy estimand, other secondary, and tertiary efficacy measures, EAS2 will be used. The treatment comparison will be based on either the 2-sided test or 95% CI.

Unless otherwise noted, the safety analyses will be conducted on the Safety Analysis Set (SS; see the definition in Section 3). Percentages will be calculated using the modified intent-to-treat (mITT) population as the denominator. For events that are sex-specific, the denominator and computation of the percentage will include only participants from the given sex.

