For continuous measures, summary statistics will include sample size, mean, standard deviation (SD), median, minimum, and maximum for both the actual and the change from baseline measurements. For certain variables that are considered to be log-normally distributed, the geometric mean and coefficient of variation (CV) will be provided instead. Either a mixed model for repeated measures (MMRM) model or an analysis of covariance (ANCOVA) model will be used to analyze continuous outcomes. Least-squares (LS) means and standard errors (SEs) derived from the analysis models will also be displayed. Treatment comparisons will be displayed showing the treatment difference LS means and the 95% CIs for the treatment differences, along with the p-values for the treatment comparisons. For certain safety laboratory measures, log-transformed values will be analyzed in the statistical model instead. The actual, change from baseline and percentage change from baseline will be presented using the derivation based on the output from the statistical model and the assumption of log-normality.

For categorical measures, summary statistics will include sample size, frequency, and percentages. Fisher's exact test or logistic regression will be used for treatment comparisons, unless otherwise stated. For laboratory values, both conventional (CN) and System International (SI) units will be presented. Therefore, both % and mmol/mol will be presented for HbA1c, and both mg/dL and mmol/L will be presented for glucose measurements.

In this study, negative binomial regression will be used to analyze the number of hypoglycemic episodes. Group mean, instead of LS mean, will be estimated, and the delta method will be used to estimate the SE of the group mean (Qu and Luo 2015). Group mean is defined as the mean response in the treatment group for the studied population. The difference between LS mean and group mean is that the LS mean estimates the response by taking the inverse link function on mean covariates, while the group mean takes the inverse link function on individual patient covariates first and then averages over all patients. For severe hypoglycemia, the empirical

method, based on exposure-adjusted rate (calculated by the total number of events divided by total exposure), may be used for treatment comparison if the number of episodes is too small and leads to convergency issues in the negative binomial regression model.

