Event rate of Level 2 hypoglycemia events (events/participant/year) • all documented	Baseline, Weeks 0-6, 0-12, 0-26, 0-52, 12-26, 26-52, and the posttreatment period	Negative binomial regression with treatment, baseline HbA1c, and baseline Level 2 hypoglycemia rate as covariates and log (exposure/365.25 days) as the offset in the model
Event rate of Level 3 hypoglycemia events (events/participant/100 years) • all documented	Baseline, Weeks 0-26, 0-52, 26-52, and the posttreatment period	Negative binomial regression with treatment and baseline HbA1c, and baseline Level 3 hypoglycemia rate as covariates and log (exposure/36525 days) as the offset in the model If the number of events is too small to run the negative binomial regression, the exposure-adjusted rate (calculated by total number of events divided by total exposure for individual participants) will be provided, and the empirical method (see Appendix 10 [Section 6.10] for details) will be used for treatment comparison.
Event rate of Level 2/3 hypoglycemia events (events/participant/year) • all documented • nocturnal, and • non-nocturnal	Baseline, Weeks 0-6, 0-12, 0-26, 0-52, 12-26, 26-52, and the posttreatment period	A negative binomial regression with treatment, baseline HbA1c, and baseline hypoglycemia rate of the same hypoglycemia type as covariates and log (exposure/365.25 days) as the offset in the model. The plots of the mean cumulative functions (MCFs) by each treatment arm will also be created. The population mean for cumulative number of events up to time t, M(t), will be estimated using a nonparametric estimation method described by Nelson ^b .
Incidence of Level 1 hypoglycemia events • all documented	Baseline, Weeks 0-6, 0-12, 0-26, 0-52, 12-26, 26-52, and the posttreatment period	Logistic regression with treatment, baseline HbA1c, and baseline Level 1 hypoglycemia incidence as covariates
Incidence of Level 2 hypoglycemia events • all documented	Baseline, Weeks 0-6, 0-12, 0-26, 0-52, 12-26, 26-52, and the posttreatment period	Logistic regression with treatment, baseline HbA1c, and baseline Level 2 hypoglycemia incidence as covariates
Incidence of Level 3 hypoglycemia events • all documented	Baseline, Weeks 0-26, 0-52, 26-52, and the posttreatment period	Logistic regression with treatment and baseline HbA1c as covariates

Endpoint	Analysis Period ^a	Statistical Method

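### The fallback p-value for the Level 3 hypoglycemia rate (SAP Appendix 11, equation 2) lacks a minus sign and can only take values from 1 to 2

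*SAP*

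**What the plan says.** SAP Section 4.6.3.1.1 analyzes the Level 3 event rate by negative binomial regression for the baseline period, Weeks 0-26, 0-52 and 26-52, and the posttreatment period. If there are too few events to run that model, "the empirical method (see Appendix 10 [Section 6.10] for details) will be used for treatment comparison". Section 4.1 is more permissive about the same fallback for severe hypoglycemia: it "may be used for treatment comparison if the number of episodes is too small and leads to convergency issues".

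The method itself is in Appendix 11 (Section 6.11). It takes the ratio of total events over total exposure in the two arms as the relative rate, estimates the variance of its logarithm as "Y_0^{-2} n_0 S_0^2 + Y_1^{-2} n_1 S_1^2", and forms a confidence interval, equation (1), on the log scale. The test follows: "The p-value for testing the null hypothesis of $H_0: \lambda = 1$ is calculated as" equation (2), which opens "p = 2\Phi\left(\left|\log(\hat{\lambda})\right|/\sqrt{\widehat{Var}(\log(\hat{\lambda" and then closes its brackets. Nothing is subtracted, and no sign precedes the absolute value. No other section gives a p-value formula for this method.

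**The concern.** A two-sided p-value should be 1 when the estimate sits on the null and should fall towards 0 as the estimate moves away. Equation (2) starts at 1 and rises. It also cannot agree with equation (1): whenever the 95% interval excludes a relative rate of 1, the printed p-value exceeds 1.95.

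At stake is a safety table. Severe hypoglycemia is a safety topic of special interest (SAP 4.6.2.1.1), and its rate is a tertiary safety endpoint. If the fallback is used and the formula is programmed as it stands, an impossible p-value would be reported beside a valid interval.

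The pointer to the method is wrong as well. Appendix 10 (Section 6.10) is the table of laboratory abnormality cut-offs, so a programmer who follows the reference finds no method there.

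**Working it through.** **Inputs**
- Equation (2) as printed: p = 2Φ(|log λ̂| / SE), null hypothesis λ = 1 (SAP 6.11).
- Reference distribution: "Assuming $\log(\hat{\lambda})$ is asymptotically from a normal distribution". The SAP does not define Φ. I read it as the standard normal cumulative distribution function, the usual convention.
- Equation (1): λ̂ × exp(±1.96 × SE) at the 95% level (SAP 6.11).
- The SAP states no p-value or expected count for this comparison, so there is no figure of its own to reproduce.

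**Step 1: range of the printed formula.** Write z = log λ̂ / SE. Since |z| ≥ 0, Φ(|z|) ≥ 0.5, so 1 ≤ p < 2, with p = 1 only when λ̂ = 1. The correct two-sided value is 2[1 − Φ(|z|)] = 2Φ(−|z|). The printed value therefore always equals 2 minus the correct one.

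| \|z\| | Printed 2Φ(\|z\|) | Correct 2[1 − Φ(\|z\|)] |
|---|---|---|
| 0 | 1.000 | 1.000 |
| 0.5 | 1.383 | 0.617 |
| 1 | 1.683 | 0.317 |
| 1.645 | 1.900 | 0.100 |
| 1.96 | 1.950 | 0.050 |
| 2.576 | 1.990 | 0.010 |
| 3 | 1.997 | 0.0027 |

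This step needs no assumed data and is enough to establish the error.

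**Step 2: conflict with equation (1), on assumed counts.** Take 30 events on LY3209590 and 10 on degludec, equal exposure, and nS² = 1.5 × events in each arm (over-dispersion factor 1.5). These figures are assumptions, chosen only to show the two equations side by side.
- Variance of log λ̂: 1.5/10 + 1.5/30 = 0.15 + 0.05 = 0.20, so SE = 0.447.
- λ̂ = 30/10 = 3.00, log λ̂ = 1.099, z = 1.099/0.447 = 2.457.
- Equation (1): 3 × exp(±1.96 × 0.447) = 1.25 to 7.21, which excludes 1.
- Equation (2) as printed: 2Φ(2.457) = 1.986. Correct value: 0.014.

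Varying the assumed over-dispersion factor:

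| Factor | z | 95% CI, equation (1) | Printed p | Correct p |
|---|---|---|---|---|
| 1 | 3.009 | 1.47 to 6.14 | 1.997 | 0.003 |
| 1.5 | 2.457 | 1.25 to 7.21 | 1.986 | 0.014 |
| 2 | 2.127 | 1.09 to 8.25 | 1.967 | 0.033 |
| 3 | 1.737 | 0.87 to 10.36 | 1.918 | 0.082 |

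In every row the correct p-value is below 0.05 exactly when the interval excludes 1. The printed value never is.

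**Step 3: second set of assumed counts.** With 335 per arm, equal exposure, 34 versus 10 events, and standard deviations of 0.45 and 0.20, λ̂ = 3.40, the interval is 1.44 to 8.04 and z = 2.79. The printed p is 1.995 and the correct p is 0.0053. With 24 versus 20 events and standard deviations of 0.35 and 0.30, λ̂ = 1.20, the interval is 0.57 to 2.54, the printed p is 1.366 and the correct p is 0.634.

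**The case against.** The strongest point on the other side is that the whole error is one small sign in a formula read from a PDF by a program, and signs can be lost that way. That is possible, so the source file should be checked. But the minus sign in the lower limit of equation (1), "\lambda} \exp\left(-z_{1-\frac{\alpha}{2}} \sqrt{\widehat{Var}(\log(\hat{\lambda", came through, and so did those in the variance exponents, so a loss at this one spot is not shown. Likewise, if Φ meant the upper-tail probability the formula would be right. That is not the usual meaning, and the SAP would have to say so.

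Second, the practical effect is small, and this stands. The method is a conditional fallback for a tertiary safety endpoint outside the multiplicity scheme. Appendix 11 supplies a correct interval, Level 3 incidence has its own logistic regression, severe events are listed individually, and a p-value above 1 gives itself away. Section 4.1 also says "The treatment comparison will be based on either the 2-sided test or 95% CI". That sentence closes the paragraph on efficacy analyses, so it is only weak support for reading a safety comparison from the interval. The interval in Appendix 11 is the better ground.

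Third, with 40 events in total the negative binomial model might well fit, so the worked examples do not show that the fallback would be reached. This is fair. They show only how the two equations behave on the same data, and the proof in Step 1 does not depend on them.

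**Conclusion.** The concern holds, as a minor one. With Φ as the standard normal distribution function, equation (2) cannot yield a value below 1 and moves the wrong way as evidence grows. It contradicts equation (1) whenever the interval excludes 1.

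The reach is limited to the Level 3 rate comparison when the negative binomial model cannot be run. The negative binomial analysis, the Level 3 incidence analysis, the interval in equation (1), and the primary and key secondary tests are unaffected. The likely harm is rework and an avoidable error in a safety table, not a hidden signal. The conclusion assumes that the printed formula matches the source PDF.

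**What to change.** Check the source PDF. If the formula stands as read here, replace equation (2) with p = 2[1 − Φ(|log λ̂|/SE)], equivalently 2Φ(−|log λ̂|/SE), and state that Φ is the standard normal cumulative distribution function. Confirm that the analysis program uses this form.

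In the Level 3 rate row of SAP 4.6.3.1.1, change the reference from Appendix 10 (Section 6.10) to Appendix 11 (Section 6.11). Two similar slips can be corrected in the same pass:
- Section 4.6.2.1.2 cites Appendix 10 (Section 6.10) for the persistent-recurrent hypoglycemia definition, which is in Appendix 9 (Section 6.9).
- Section 4.1 labels Section 6.13 as Appendix 12, but it is headed Appendix 13.

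The cost is one corrected line, the cross-references and one program check. Design, data collection and sample size do not change. Section 4.1 allows method changes to be recorded in the SAP or the clinical study report, so a short note would do.

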6.12. Appendix 12: Interaction Effect for Subgroup Analysis – Treatment Regimen Estimand

The ANCOVA analysis will be performed within each subgroup with multiple imputation of missing primary measures. Statistical inference over multiple imputation of missing data will be guided by Rubin (1987) to obtain $\hat{\theta}_1$ and $se(\hat{\theta}_1)$ for the treatment difference in subgroup 1, and $\hat{\theta}_2$ and $se(\hat{\theta}_2)$ in subgroup 2. Then, the distribution of treatment by subgroup interaction (difference of treatment effects) is: $\hat{\theta}_1 - \hat{\theta}_2 \sim N\left(\theta_1 - \theta_2, [se(\hat{\theta}_1)]^2 + [se(\hat{\theta}_2)]^2\right)$

A z-statistic can be contrasted such that $z = \frac{\hat{\theta}_1 - \hat{\theta}_2}{\sqrt{[se(\hat{\theta}_1)]^2 + [se(\hat{\theta}_2)]^2}} \sim N(0,1)$, under the null hypothesis of no treatment by subgroup interaction.

For k groups ($k \geq 2$),

let $\hat{\boldsymbol{\theta}} = (\hat{\theta}_1, \hat{\theta}_2, \dots, \hat{\theta}_k)$ and $Var(\hat{\boldsymbol{\theta}}) = diag([se(\hat{\theta}_1)]^2, [se(\hat{\theta}_2)]^2, \dots, [se(\hat{\theta}_k)]^2)$.

A chi-square test (with degrees of freedom = $k-1$) can be constructed as

$$T = (C\hat{\boldsymbol{\theta}})'(CVC')^{-1}(C\hat{\boldsymbol{\theta}}) \sim \chi_{k-1}^2$$

where C is a matrix of contrast such that

$$C = \begin{bmatrix} -1 & 1 & 0 & \dots & 0 & 0 \\ 0 & -1 & 1 & \dots & 0 & 0 \\ \dots & \dots & \dots & \dots & \dots & \dots \\ 0 & 0 & 0 & \dots & -1 & 1 \end{bmatrix}$$

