Analysis Model	After the imputation, the observed and imputed data will be analyzed by the ANCOVA model using treatment, strata (country, CGM use prior to study entry [yes/no], and carbohydrate counting for prandial insulin dosing [yes/no]), and baseline value of the dependent variable as independent variables. The statistical inference will be based on the multiple imputation framework by Rubin ^b .	The MMRM model will include treatment, strata (country, baseline, CGM use prior to study entry [yes/no], and carbohydrate counting for prandial insulin dosing [yes/no]), and visit and treatment-by-visit interaction as fixed effects and baseline of the dependent variable as a covariate. The Kenward-Roger approximation will be used to estimate denominator degrees of freedom for the MMRM models. An unstructured covariance structure will be used to model the within-participant errors. If this structure fails to converge, the following covariance structures will be used in order until one converges: 
 1. Toeplitz with heterogeneity 2. autoregressive with heterogeneity 3. compound symmetry with heterogeneous variances 4. Toeplitz 5. Autoregressive, and 6. compound symmetry without heterogeneous variances.

Abbreviations: ANCOVA = analysis of covariance; CGM = continuous glucose monitoring; EAS1 = Efficacy Analysis Set 1; HbA1c = hemoglobin A1c; EAS2 = Efficacy Analysis Set 2; MMRM = mixed model of repeated measures.

^a (Qu and Dai 2022)

^b (Rubin 1987)

The 2-sided 95% CI of the LS mean difference (LY3209590 - insulin degludec) in the HbA1c change from baseline to Week 26 (Visit 22) will be estimated. For both estimands, LY3209590 will be declared noninferior to insulin degludec if the upper limit of the 2-side 95% CI for the LS mean difference in the HbA1c (measured in %) change from baseline is below the NIM of +0.4%. In addition, the 95% CI for the LS mean difference will be compared to an alternative NIM of +0.3%.

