4.7.2. Subgroup Analyses

The interaction effects will be evaluated using a significance level of 0.05, unadjusted. Subgroup analyses will be conducted as defined in this section. Additional subgroup analysis may also be performed as appropriate.

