4.7.2.1. Subgroup Analysis for HbA1c

The subgroups for analyzing HbA1c and change in HbA1c from baseline to Week 26 will be defined as (a subgroup category will not be included if there are less than 10 participants in the category)

- baseline HbA1c stratum (<8.0% and $\geq 8.0\%$)
- region (US and non-US)
- region (North America, South America, Europe, Asia)
- age as (<40 years and ≥ 40 years)
- age as (<65 years and ≥ 65 years)
- CGM use prior to study entry (yes and no)
- carbohydrate counting for prandial insulin dosing (yes and no)
- gender (female and male)
- ethnicity (Hispanic or Latino, Not Hispanic or Latino)
- race (White, Asian, American Indian or Alaska Native, Native Hawaiian or Other Pacific Islander, and Black or African American)
- estimated Glomerular Filtration Rate (eGFR) at baseline (<60, ≥ 60 to <90 and ≥ 90 mL/min/1.73 m²), and
- duration of diabetes (<median and \geq median).

For treatment regimen estimand: Analyses for HbA1c and its change will be performed using the same ANCOVA model with the same independent variables as described in Section 4.3.2, separately for each subgroup. The missing values will be imputed by multiple imputation method same as the primary analysis for treatment regimen estimand. The statistical inference will be based on the multiple imputation framework by Rubin (1987). The p-value for treatment by subgroup interaction will be calculated using a chi-square test based on estimated treatment differences within each subgroup (see details in Appendix 12 [Section 6.12]).

For efficacy estimand: Analyses for HbA1c and its change will be performed within each subgroup using the same MMRM model for the efficacy estimand described for the primary analysis in Section 4.3.2. In addition, the interaction effects be assessed using the model will include the same fixed effects given for the primary analysis model plus factors of subgroup, 2-way interaction of subgroup and treatment, 2-way interaction of subgroup and visit, and 3-way interaction of treatment, visit, and the subgroup.

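### The treatment-regimen subgroup interaction test uses a large-sample reference but admits categories as small as 10, where its 5% level is not held

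*SAP*

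**What the plan says.** SAP 4.7.2.1 analyses HbA1c by twelve subgroup factors. For the treatment-regimen estimand it does so "using the same ANCOVA model with the same independent variables as described in Section 4.3.2, separately for each subgroup". Section 4.3.2 defines that model as an "ANCOVA model using treatment, strata (country, CGM use prior to study entry [yes/no], and carbohydrate counting for prandial insulin dosing [yes/no]), and baseline value" of HbA1c. Missing values are imputed as in the primary analysis and combined by Rubin's rules.

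The interaction p-value is obtained "using a chi-square test based on estimated treatment differences within each subgroup". Appendix 12 gives the detail: "The ANCOVA analysis will be performed within each subgroup with multiple imputation of missing primary measures". For two subgroups, the difference in estimated effects divided by the root of the summed squared standard errors is taken as N(0,1). For k subgroups: "A chi-square test (with degrees of freedom = $k-1$) can be constructed as". No residual degrees of freedom, Rubin degrees of freedom, t or F reference appears.

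The only protection against small categories is in 4.7.2.1: "a subgroup category will not be included if there are less than 10 participants in the category". A category of exactly 10, both arms together, therefore enters the test. On the level, 4.7.2 says: "The interaction effects will be evaluated using a significance level of 0.05, unadjusted".

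**The concern.** A normal or chi-square reference is right when each subgroup's standard error is estimated precisely. In a category of 10, the ANCOVA spends at least five parameters, plus one for each further country, so the residual variance rests on a handful of degrees of freedom. When that variance happens to come out too small, the category looks different from the rest and the test signals an interaction that is not there.

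The affected estimand is the one for the US submission. Race, with five listed categories, is the factor most open to small cells, and the SAP version history says its categories were updated after FDA feedback, so this output will be read. The SAP's other two subgroup interaction tests (the efficacy-estimand MMRM and the hypoglycemia rate model) each use a single joint model. This one does not. Appendix 11 itself warns, for event rates, that an underestimated variance can inflate the type 1 error.

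**Working it through.** **Inputs from the documents.** Level 0.05 (SAP 4.7.2); smallest category 10 (4.7.2.1); ANCOVA terms (4.3.2); reference N(0,1) or chi-square with k-1 degrees of freedom (Appendix 12); about 670 randomized 1:1, SD 1.1 (SAP section 5).

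**Assumed.** Sizes of the categories, number of countries within a small category, and the proportion of Week 26 HbA1c missing.

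**Step 1: the stated 5%.** The chi-square(1) critical value 3.841 gives 5.0% in large samples. Simulating the Appendix 12 statistic under no interaction with subgroups of 330 and 340, complete data, gives 5.2-5.3%. The stated level holds when both groups are large.

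**Step 2: residual degrees of freedom at n = 10.** Intercept, treatment, CGM use, carbohydrate counting and baseline use 5 parameters; c countries add c - 1. Residual df = 10 - 5 - (c - 1) = 6 - c.

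**Step 3: why the small category dominates.** Ignoring covariates, the variance of a treatment difference is 4 × SD²/n. For n = 10 it is 4 × 1.21/10 = 0.484; for n = 660 it is 4 × 1.21/660 = 0.0073. The small category carries 0.484/0.4913 = 98.5% of the variance, so the z-statistic behaves almost like a t on the small category's residual df, and the true size is close to P(|t| > 1.96).

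| Countries in the category of 10 | Residual df | P(\|t\| > 1.96) | Simulated, 10 vs 660, complete data |
|---|---|---|---|
| 1 | 5 | 10.7% | 10-11% |
| 2 | 4 | 12.2% | about 12% |
| 3 | 3 | 14.5% | 14% |
| 4 | 2 | 18.9% | 17-18% |

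**Step 4: other splits, complete data.**
- Four race categories of 500/130/25/12: about 8-12% with one to four countries.
- Five race categories, two of them of size 10: 13-23% with one to four countries.
- Smallest category 20: about 7-9%. Smallest category 30: about 6-7%. Smallest category 50: about 5-6%.

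**Step 5: with return-to-baseline imputation, 10 vs 660, one to five countries.** 5% missing: 9-18%. 10% missing: 7-15%. 15% missing: 5-12%. Rubin's variance is conservative here: with 15% missing, 330 vs 340 rejects only about 2% of the time. A figure near 5% for the small category is therefore two errors partly cancelling.

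**Step 6: candidate repairs.**
- In the 10 vs 660 complete-data sets, a Satterthwaite t on the existing statistic gives 4.7-5.5%, and one joint ANCOVA with a treatment-by-subgroup term gives 4.8-5.3%.
- The joint result used a common SD of 1.1. With an assumed SD of 1.5 in small groups and 1.1 in large ones, the joint F test rejects about 11-16% of the time, against about 6-12% for Appendix 12 as written.
- A Welch-type F on the existing statistic gave about 4-7% in the scenarios run for it, equal and unequal SD.

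**The case against.** Several points on the other side stand.

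- **Size.** A reader might infer that the interaction test in this trial will run at 12-20%. The documents do not support that. They give no race distribution and no country count per category, and the specified analysis includes multiple imputation, which offsets part of the excess under return-to-baseline. Retrieved-dropout imputation, the SAP's first choice, was not simulated. Nor does the 15% dropout assumption fix the missing fraction, since participants who stop treatment are asked to stay in follow-up.
- **Scope.** A reader might infer that every subgroup test is affected. Most of the twelve factors, such as CGM use, gender and median duration of diabetes, show no evident reason to yield cells near 10. Even for race, small cells are likely rather than documented.
- **Stakes.** A reader might infer a threat to the trial's conclusions. There is none: the interaction tests are unadjusted and outside the alpha-controlled family. With twelve tests at an exact 5%, treated as independent, at least one false signal has probability 1 - 0.95^12 = 46% anyway.
- **Cross-estimand comparison.** A reader might infer that any disagreement between the two estimands' interaction tests would be an artefact of this reference distribution. The estimands also differ in data set and missing-data handling, so that cannot be concluded.
- **Remedy.** The joint model is not automatically better. Separate fits allow each subgroup its own residual variance, which is a real advantage. The efficacy estimand's joint model is an MMRM without imputation, so it is no precedent for Rubin pooling.

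None of this removes the mismatch between a minimum of 10 participants and a reference that assumes known standard errors.

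**Conclusion.** The concern holds in a limited form. As written, SAP 4.7.2.1 and Appendix 12 do not deliver the stated 0.05 level when a category is near the minimum of 10. The 10-18% range applies to one such category in one to four countries on complete data, and the excess is small once all categories reach 30. Those figures rest on the assumed sizes, country counts and SD of 1.1, and on simulations without retrieved-dropout imputation. The practical risk is a spurious finding that the treatment effect differs by a sparsely filled factor, most plausibly race, in the treatment-regimen results. It is worth correcting because the repair is cheap, but nothing in the primary or key secondary inference depends on it.

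**What to change.** Amend SAP 4.7.2.1 and Appendix 12 as follows.

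1. Keep the within-subgroup fits and the Appendix 12 statistic, but replace the N(0,1)/chi-square reference with a finite-df one: a Satterthwaite t for two subgroups and a Welch-type F for k subgroups. Use for each subgroup the small-sample Rubin degrees of freedom, which take account of the residual df of its fit.
2. Leave out of the test any category whose ANCOVA leaves too few residual df to estimate its standard error, and state that minimum in terms of residual df rather than participants. Such categories can still be shown descriptively. This is needed alongside step 1, because a Welch approximation is itself rough when several categories have only one or two residual df.
3. If a joint ANCOVA with a treatment-by-subgroup term is wanted, present it as supporting, and say that its F test assumes a common residual variance and can be inflated if small subgroups are more variable.

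The cost is SAP wording and a few lines of programming, with no new data. Interaction p-values become slightly larger, with a little less power where small categories are involved.
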